#### **VARIABLES TO BE STUDIED:**

- Basic demographics: Age, sex, ethnicity, income status, BMI, educational level.
- Pertinent medical history: Comorbidities including history of diabetes, stroke, Parkinson’s disease, hypertension, thyroid disease, constipation, ASA class, opiate use, TCA use, history of IBD, poor preparation in previous colonoscopies (yes/no), Charleston comorbidity index, use of anti-emetics for the bowel cleansing (yes/no).

- Procedure details: Date, indication, bowel preparation quality (reported as BPPS), type of sedation, start time of the procedure, the end time of the procedure, cecal intubation (yes/no), cecal intubation time and withdrawal time.

### **DATA MANAGEMENT:**

- Study data will be collected and managed using REDCap (Research Electronic Data Capture). REDCap is a secure, web application designed to support data capture for research studies, providing user-friendly web-based case report forms, real-time data entry validation (e.g. for data types and range checks), audit trails and a de-identified data export mechanism to common statistical packages (P/MCS, SAS, Stata, R/S-Plus). The system was developed by a multi-institutional consortium which includes Cleveland Clinic and was initiated at Vanderbilt University. The database is hosted at the Cleveland Clinic Datacenter. The system is protected behind a login and Secure Sockets Layer (SSL) encryption. There is an audit trail tracking all logins and activities in the database. Data collection is customized for each study or clinical trial based on a study-specific data dictionary defined by the research team with guidance from the REDCap administrator in Quantitative Health Sciences at the Cleveland Clinic.
- Any unintended data breaches will be immediately reported to the institutional IRB. Data analysis will be performed by a member of the Department of Quantitative Health Sciences, Lerner Research Institute.
- In this study, no elements have been identified with foreseeable risks to participants. A list of randomly generated participant numbers will be utilized for all patient identification, data collection and data analysis by the research team. Patients' data will be identified by these numbers when key study personnel work with the data. The list linking participant numbers to patient medical record numbers will be stored in a secure, locked environment and will only be utilized to re-verify data. The study will utilize de-identified data for data analysis and reporting.
- Participants will be recruited for this study and will have to be able to provide consent for the colonoscopy procedure and for inclusion in the trial. All participants will also have to agree to complete the survey. Data will be collected from institutional EMR (EPIC) for details on patients' demographics, laboratory results, and procedure details. This is related to customary clinical duties carried out by residents, fellows, and staff during the course of their education and employment at Cleveland Clinic.

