### **ASSESSMENT OF PATIENT TOLERABILITY AND ADVERSE EFFECTS:**

Each patient will be provided a survey at the time of enrollment. The patients will be instructed to complete the survey in “real time” (as they are drinking the preparation). The co-investigator or the study coordinator will collect the survey from the patient prior to receiving sedation for their colonoscopy procedure. The co-investigator or study coordinator will review the survey to ensure all questions are answered.

The purpose of the survey will be to document the following information:

- a. Demographic details (including level of education and annual income),
- b. The start time and end time of the ingestion of bowel cleansing agent,
- c. Total amount of the cleansing agent ingested (to be recorded using a visual depiction of the remaining bowel preparation agent in the container),
- d. Full dose of the bowel cleanser ingested (yes versus no),
- e. Details including the type and timing of symptoms encountered (nausea, vomiting, abdominal pain, bloating, thirst, dizziness, headache or paresthesia),
- f. If any of the above-mentioned symptoms were present prior to the start of the cleansing process, did the use of the purgative agent make them worse (yes versus no),
- g. Ease of use based on a modified 5-point Likert scale: “very easy,” “easy,” “tolerable,” “difficult,” or “very difficult” (score 5–1, respectively),
- h. Palatability based on a modified 5-point Likert scale: “very good,” “good,” “fair,” “bad,” or “worst” (score 5–1, respectively), – *Patients who score ≥3 points in items h) and i) will be classified as the tolerant group.*
- i. Willingness to use the same agent again (yes versus no),

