### **BOWEL PREPARATION AGENTS:**

#### **CLENPIQ (SP/MC):**

##### **INDICATIONS/CONTRAINDICATIONS:**

The use of CLENPIQ will be studied in our project and compared to the standard of care which is golytely (4 L PEG-ELS). CLENPIQ is a combination of sodium picosulfate, a stimulant laxative, and magnesium oxide and anhydrous citric acid (SP/MC) which form magnesium citrate, an osmotic laxative, indicated for cleansing of the colon as a preparation for colonoscopy in adults. Contraindications to CLENPIQ use include 1) patients with severely reduced renal function (creatinine clearance less than 30 mL/minute) which may result in accumulation of magnesium, 2) gastrointestinal obstruction or ileus, 3) bowel perforation, 4) toxic colitis or toxic megacolon, 5) gastric retention, and 6) an allergy to any of the ingredients in CLENPIQ.

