### **DRUG INTERACTIONS:**

Use caution when prescribing CLENPIQ for patients with conditions or who are taking medications that increase the risk for fluid and electrolyte disturbances or may increase the risk of renal impairment, seizure, arrhythmias, and prolonged QT in the setting of fluid and electrolyte abnormalities. This includes patients receiving drugs which may be associated with hypokalemia (such as diuretics or corticosteroids, or drugs where hypokalemia is a particular risk, such as cardiac glycosides) or hyponatremia. Use of caution is also advised when CLENPIQ is used in patients with severe active colitis, on nonsteroidal anti-inflammatory drugs (NSAIDS) or drugs known to induce Antidiuretic Hormone Secretion (SIADH), such as tricyclic antidepressants, selective serotonin re-uptake inhibitors, antipsychotic drugs and carbamazepine, as these drugs may increase the risk of water retention and/or electrolyte imbalance.

It is important to note that oral medications administered within one hour of the start of administration of CLENPIQ solution may be flushed from the GI tract and the medication may not be absorbed. Tetracycline and fluoroquinolone antibiotics, iron, digoxin, chlorpromazine, and penicillamine, should be taken at least 2 hours before and not less than 6 hours after administration of CLENPIQ to avoid chelation with magnesium. Prior or concomitant use of antibiotics with CLENPIQ may reduce the efficacy of CLENPIQ as conversion of sodium picosulfate to its active metabolite BHPM is mediated by colonic bacteria.

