#### **ADVERSE EFFECTS:**

Nausea, abdominal fullness and bloating are the most common adverse reactions (occurred in up to 50% of patients) to the administration of golytely. Abdominal cramps, vomiting and anal irritation occurs less frequently. These adverse reactions are transient and usually subside rapidly. Cases of urticaria, rhinorrhea, dermatitis and (rarely) anaphylactic reaction have been reported which may represent allergic reactions.

Published literature also contains isolated reports of serious adverse reactions following the administration of PEG-electrolyte solution products in patients over 60 years of age which include upper GI bleeding from Mallory-Weiss Tear, esophageal perforation, asystole, sudden dyspnea with pulmonary edema, and “butterfly-like” infiltrates on chest X-ray after vomiting and aspirating PEG.

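### The statement that no foreseeable risks were identified conflicts with the protocol's own drug sections, and serious adverse events have no defined collection, reporting path or by-arm summary

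*Combined protocol and SAP*

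**What the plan says.** - **Data Management** opens its bullet on participant numbers and de-identification with: "In this study, no elements have been identified with foreseeable risks to participants". The bullet before it contains the only IRB reporting rule in the text: "Any unintended data breaches will be immediately reported to the institutional IRB". A later bullet says that demographics, laboratory results and procedure details will be taken from the electronic medical record (EMR).
- **Clenpiq, Drug Interactions** advises caution in patients whose conditions or medicines raise fluid and electrolyte risk or "may increase the risk of renal impairment, seizure, arrhythmias, and prolonged QT in the setting of fluid and electrolyte abnormalities". **Clenpiq, Indications/Contraindications** says of severely reduced renal function: "which may result in accumulation of magnesium".
- **Golytely, Adverse Effects** says: "Cases of urticaria, rhinorrhea, dermatitis and (rarely) anaphylactic reaction have been reported". It also cites isolated reports in patients over 60 of "upper GI bleeding from Mallory-Weiss Tear, esophageal perforation, asystole, sudden dyspnea with pulmonary edema", and of lung infiltrates after vomiting and aspiration.
- **Assessment of Patient Tolerability and Adverse Effects** describes one instrument, a survey that patients fill in while drinking the preparation. It lists eight symptoms: nausea, vomiting, abdominal pain, bloating, thirst, dizziness, headache and paresthesia. It also asks whether pre-existing symptoms got worse. Staff collect it before sedation and "review the survey to ensure all questions are answered".
- **Secondary Outcomes**, **Statistical Analysis** and **Variables to Be Studied** contain no safety outcome, no adverse-event analysis and no safety variable.

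**The concern.** There are two separate problems. First, a protocol cannot say that it found no foreseeable risks to participants and also list serious risks of both study preparations. Anyone relying on the Data Management sentence alone would be misinformed.

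Second, the described collection does not reach the kind of event that the drug sections warn about. A self-completed form that closes before sedation cannot record what happens during or after the procedure, and a patient who becomes too ill to write will not complete it. The Introduction argues for SP/MC partly on a lower incidence of adverse events, and the Impact section aims to show that inpatients gain the same benefit as outpatients. At stake is whether a trial of 1000 hospitalised patients can describe serious harms by preparation at all.

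**Working it through.** No figure in the plan is disputed. The check sets sections against each other and then asks what is lost.

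**1. The risk statement against the drug sections.**
- Data Management: no foreseeable risks, with no limit to data or confidentiality.
- SP/MC: renal impairment, seizure, arrhythmia and prolonged QT, linked to fluid and electrolyte disturbance; magnesium accumulation when renal function is severely reduced.
- PEG-ELS: anaphylactic reaction (rare); upper GI bleeding, esophageal perforation, asystole, and pulmonary edema and infiltrates with aspiration (isolated reports, patients over 60).

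A risk that the protocol itself names is foreseeable. Taken literally, the statements conflict.

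**2. Whether the exclusions remove these risks.** The Inclusion/Exclusion Criteria exclude creatinine clearance below 30 ml/min, symptomatic heart failure, arrhythmia, obstruction, ileus, perforation, toxic megacolon and known allergy. That largely covers magnesium accumulation and reduces several other risks. However, there is no upper age limit, and patients on the medicines for which the Clenpiq section urges caution (for example diuretics, corticosteroids, NSAIDs, tricyclics) are not excluded. Variables to Be Studied records tricyclic use, so such patients are expected to enrol. The risks are reduced, not removed.

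**3. Routes by which a serious event could enter the dataset.**
- Survey: eight symptoms, closed before sedation, dependent on the patient.
- EMR laboratory results: could show renal or electrolyte changes, but no tests, timing or safety use are stated.
- EMR procedure details: Variables to Be Studied lists timing, sedation, indication, preparation quality and cecal intubation, and no complications.
- Outcomes and analysis: no safety item.

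No listed route records a serious event as an adverse event.

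**4. What complete capture would allow.** Inputs: 1000 patients, 250 per group (Sample Size Calculation). Both randomisation schemes in Study Design, 1:1:1:1 and 1:1, split evenly by agent, so assume 500 per agent. With zero events among n patients, the one-sided 95% upper bound is 1 − 0.05^(1/n):
- n = 250: 1 − 0.05^(1/250) = 1.2%
- n = 500: 1 − 0.05^(1/500) = 0.6%
- n = 1000: 1 − 0.05^(1/1000) = 0.3%

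These bounds require that every patient was checked. Without that, no bound can be stated.

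**5. Whether any event is likely.** The documents give no serious-event rate. For assumed rates p, the chance of at least one event in 1000 patients is 1 − (1 − p)^1000:
- p = 0.1%: 63%
- p = 0.2%: 86%
- p = 0.5%: 99%

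These rates are illustrative only. They show that even an uncommon event would probably occur at least once.

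**The case against.** The strongest reply is about context. The sentence stands among bullets on data breaches, linking lists and de-identification, and was plausibly meant for data risk. The exclusions and the instruction to follow the approved labels show that the authors did consider drug risk. The serious events are described as rare, isolated or tied to particular patients. Much of this stands: the first problem may be only one badly placed sentence. It still has to be changed, because its wording covers risks to participants without limit.

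The second reply is that silence is not prohibition. Institutional reporting rules may apply, and consent pages are not part of the text available. That is fair, but the text cites no such rule, and an IRB duty would not by itself supply collection or analysis by arm.

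The third reply is that no safety conclusion is planned. The hypotheses concern cleansing, and the outcomes add tolerability, repeat procedures and rescue medication. That also stands, and the primary analysis is unaffected.

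A reader might infer three stronger things that the documents do not support:
- That serious-event procedures are absent because of the no-risk sentence. Nothing links the two.
- That only data breaches go to the IRB. The text states that one rule and is silent on others.
- That adverse effects are not collected at all. The survey records symptoms with their timing, and laboratory results are abstracted.

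Nor can a number of missed events be given, since the documents offer no rate.

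**Conclusion.** The point holds in two independent parts. The Data Management sentence, as worded, contradicts the Clenpiq and Golytely sections, and these must be reconciled. The available text also provides no serious-event definition, collection window, IRB reporting path or by-arm safety summary. Followed as written, serious events during or after the procedure, or in patients unable to complete the survey, have no defined route into the dataset as adverse events, so the trial could not describe serious harms by preparation.

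The loss is the ability to state any bound, where complete capture with zero events would give about 0.6% per agent. That figure assumes 500 patients per agent and full ascertainment. The finding is limited to the text available and does not touch the cleansing endpoint.

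**What to change.** 1. In Data Management, either restrict the sentence to data-handling risk or replace it with the risks already named in the Clenpiq and Golytely sections.
2. Define serious adverse events.
3. Abstract them from the EMR already in use, for every randomised patient from first dose to discharge, whether or not a survey exists. State which laboratory results are taken, when, and for what safety purpose.
4. State the IRB reporting path for serious adverse events.
5. Add to Statistical Analysis a table of serious adverse events by randomised group, covering all six groups in Study Design.

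The cost is a protocol amendment, one extra REDCap form and a few minutes of chart abstraction per patient by existing staff. The stated risk profile becomes less favourable. Dose, schedule, sample size and the primary analysis do not change.
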